##### **7.1.2.1 Participants and y recruitment**

Initial contact and recruitment of participants will be done at different sale points, such as convenience stores, mini supers (Oxxo, Extra, 7 Seven), and retail stores located in different points of Mexico City. The selection of the sale points will be done by convenience, and will include those located in AGEBS (the Mexican equivalent for census tracts) classified as of intermediate socioeconomic level (3, 4 or 5) according to INEGI (National Institute of Statistic and Geography) [42].

An initial questionnaire will be used to explore eligibility criteria, including general demographic information (age, sex, information contact), consumption and purchase habits, as well as a series of questions to determine the individual socioeconomic level (Appendix 1). This rule is an algorithm developed by the Committee of Socioeconomic Levels and measures the extent in which the most important needs of households are satisfied by considering eight characteristics or possessions of the household and schooling of the person who most contributes to household expenses. The eight variables are: 1) schooling of the person who most contributes to expenses, 2) number of rooms, 3) number of bathrooms, 4) number of lamps/bulbs, 5) number of automobiles, 6) possession of a shower, 7) possession of a stove, and 8) Type of flooring. As a result, this rule produces an index that ranks households into seven levels, from A (highest socioeconomic level) to E (lowest socioeconomic level).

The questionnaire will be applied randomly with a systematic skip (every 5 consumers) at the exit of the sale point, after a brief explanation of the study objectives and informed consent. Participants classified as typical C or lower C and meeting inclusion criteria will be invited to participate in focus groups (see below).

There will be a total of five focus groups with an average of 5 to 10 participants each, which often buy and consume (twice a week), at least two of the categories of prepackaged meals and bottled beverages of interest for the study (mentioned in section 8.1.1.2) and meet the following inclusion criteria:

- **Group 1:** Men and women 13 to 15 years old that visit the sales point by themselves, with a specific budget to purchase products.

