- **Group 2:** Men and women 21 to 23 years old, who visit the sales point at least twice a week, purchase these types of foods and/or beverages, for their own consumption and/or their family.
- **Group 3:** Women, mothers of 3 to 12 year old children who visit the sales point at least twice a week, purchase these types of foods and/or beverages, for their own consumption and/or their family.
- **Group 4:** Men, fathers of 3 to 12 year old children who visit the sales point at least twice a week, purchase these types of foods and/or beverages, for their own consumption and/or their family.
- **Group 5:** Men and women 55 to 70 years old who visit the sales point at least twice a week, purchase these types of foods and/or beverages, for their own consumption and/or their family.

Group 1 participants (Men and women from 13 to 15 years) will be contacted only if they attend the recruitment points accompanied by a parent or guardian. Participants who meet the inclusion criteria will be invited to participate voluntarily in the focus groups, indicating the day, time, place and duration of the event, as well as the incentive they will receive in return for their participation. Candidates who agree to participate in the study will receive at least three reminders via text message or phone call about the date and location of the focus groups. Group 1 participants will be asked to attend with a parent or guardian.

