#### **7.1.2.3.2 Quantitative Information**

Once the focus group Guide has been completed, a questionnaire evaluating the acceptability and understanding of the different FoPNL Systems will be applied (See Appendixes). The questionnaire has been designed considering the different aspects that determine the acceptability of a system (18), as well as previous experiences recently published exploring acceptability and understanding of a new proposal of Front of Pack Labelling in European consumers [21]. The questionnaire consists of 26 items divided in three sections: 1) Demographic Information. 2) Acceptability of the FoPNL Systems proposals, and 3) Objective understanding of the Front of Pack Labelling.

**Acceptability:** Participants will be asked to select the label that best corresponds to a series of affirmations. A total of four items will evaluate liking of the label, three items will evaluate the attractiveness of the label, and four items will explore perceived cognitive load.

**Objective Understanding.** Participants will classify three products according to their nutritional quality, using the different FoPNL systems evaluated. For this purpose, images of three products of the same food category (previously selected during the exercises with the nutritional profiling system) displaying one of the FoPNL will be shown. Participants will classify the products according to their nutritional quality. No other nutritional information will be provided. The classification will be considered correct if all three products are ranked

in the expected order, based on their nutritional quality. The same five food categories used in the exercises of nutritional profiling explained in section 8.1.1.2 will be tested.

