#### **7.1.2.6 Data analysis**

##### **7.1.2.6.1 Analysis of quantitative data**

The analysis will be carried out using the statistical package Stata version 14. Descriptive tabulation of demographic data will be made through an estimation of means and standard deviations (or medians and interquartile ranges in case of variables with non-parametric distribution) for quantitative variables, as well as proportions for categorical variables.

To evaluate label acceptability, the percentage of participants who selected each one of the proposed labels in relation to liking, attractiveness and perceived cognitive load of the label will be calculated. To compare the performance of the label in respect to objective understanding, the percentage of correct responses by labelling system, will be calculated. These ratios will be calculated also by food category and by sub-groups (for example, schooling, sex). The differences by category will be explored using Chi square tests.

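### Ordinary chi-square is the only test named for objective understanding, but the same 25 to 50 people answer under several labels; its error rate is wrong in any test to which a person contributes more than one correlated answer (minor)

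*Combined protocol and SAP*

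**What the plan says.** All references are to the combined protocol and SAP.

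- **Analysis (7.1.2.6.1).** "To compare the performance of the label in respect to objective understanding, the percentage of correct responses by labelling system, will be calculated". The next sentence adds splits by food category and by subgroups such as schooling and sex. Then comes the only test: "The differences by category will be explored using Chi square tests". No paired, repeated-measures or cluster-adjusted method is named.
- **Task (7.1.2.3.2).** "Participants will classify three products according to their nutritional quality, using the different FoPNL systems evaluated". A ranking counts as correct only if all three products are in the expected order. On foods: "The same five food categories used in the exercises of nutritional profiling explained in section 8.1.1.2 will be tested".
- **People (7.1.2.1).** "There will be a total of five focus groups with an average of 5 to 10 participants each".
- **Labels.** At most six in Phase 1 (7.1.1.1); three new designs go into Phase 2 (7.1.3), which repeats the Phase 1 methodology (7.2.1).
- **Use of the results (7.2.2).** The two best-evaluated proposals are chosen from the focus groups and the questionnaire together. No p-value rule is given.

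**The concern.** What is summarised is a percentage of responses, not of people. Pearson's chi-square assumes that every response is independent. Ranking products is partly a skill, so one person's answers are likely to be correlated, and the test then has the wrong variance.

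The direction depends on the contrast. If several answers per person are pooled and men are compared with women, chi-square overstates the information, and a label can seem to work worse in one sex or schooling group by chance. If foods are compared within the same people, chi-square ignores the pairing, and a real difference between foods can be missed. If labels are tested on answers pooled over foods, the p-value may be too small or too large, and the reader cannot tell which.

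**Working it through.** The plan states no error rate, power or sample size for these tests, so there is no figure to reproduce.

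**Inputs from the document**
- People: 5 × 5 = 25 to 5 × 10 = 50.
- Labels: up to six (Phase 1), three (Phase 2). Food categories: five.
- Questionnaire: 26 items. Acceptability takes 4 + 3 + 4 = 11, which leaves at most 26 − 11 = 15 for rankings and demographics together.

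**Number of rankings per person.** A full crossing needs 3 × 5 = 15 rankings for three labels and 6 × 5 = 30 for six. At one ranking per item, 30 do not fit, and 15 leave no demographic item. A full crossing would therefore need several rankings per item. The supplied text does not settle this, so results are given for different numbers of answers, m.

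**Assumptions.** N = 40, 60% correct, within-person intraclass correlation (ICC) 0.1, 0.2 or 0.3, and a two-sided 5% level. The document states 0.05 only for the Phase 3 regression (7.3.6).

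**1. Two equal subgroups, m pooled answers per person.** The chi-square statistic is inflated by 1 + (m − 1) × ICC, so the false positive rate is about 2 × [1 − Φ(1.96 / √(1 + (m − 1) × ICC))]. For m = 5 and ICC = 0.2, the factor is 1 + 4 × 0.2 = 1.8, 1.96 / √1.8 = 1.46, and the rate is 0.144.

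| Answers pooled | Formula, ICC 0.1 / 0.2 / 0.3 | Simulation (40,000 runs) |
|---|---|---|
| 1 | 0.050 / 0.050 / 0.050 | 0.049 / 0.047 / 0.049 |
| 2 | 0.062 / 0.074 / 0.086 | 0.065 / 0.077 / 0.092 |
| 3 | 0.074 / 0.098 / 0.121 | 0.076 / 0.099 / 0.126 |
| 5 | 0.098 / 0.144 / 0.186 | 0.101 / 0.146 / 0.192 |

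A t-test on the per-person number correct gives 0.050 to 0.053.

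**2. Five foods within one label, one answer each.** The statistic shrinks by (1 − ICC), so the rate is P(χ² with 4 df > 9.488 / (1 − ICC)) = 0.032 / 0.018 / 0.009. Simulation gives 0.034 / 0.018 / 0.010, and Cochran's Q 0.047 to 0.049. With true rates of 50, 55, 60, 70 and 75% correct, chi-square has power 52% against 66% for Q at latent correlation 0.3, and 49% against 74% at 0.5.

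**3. Labels, one answer per label.** The same shrinkage applies. At ICC 0.2 the rate is 0.024 for three labels and 0.017 for six.

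**4. Labels pooled over five foods (if fully crossed).** With person / person-by-label variances of 0.3/0, 0.3/0.1 and 0.2/0.2 out of a total latent variance of 1:

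| Test | Three labels | Six labels |
|---|---|---|
| Chi-square | 0.025 / 0.065 / 0.125 | 0.018 / 0.070 / 0.166 |
| Cochran's Q on person-by-food blocks | 0.051 / 0.105 / 0.159 | 0.048 / 0.139 / 0.231 |
| Repeated-measures F on per-person scores | 0.049 / 0.051 / 0.050 | 0.047 / 0.048 / 0.052 |
| Friedman on per-person scores | 0.051 / 0.050 / 0.050 | 0.047 / 0.048 / 0.051 |

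So chi-square can err either way, and Cochran's Q is not a general replacement.

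**5. Focus group.** "Once the focus group Guide has been completed, a questionnaire evaluating the acceptability and understanding of the different FoPNL Systems will be applied", so answers may also cluster by group. Group 3 is all women ("Women, mothers of 3 to 12 year old children who visit the sales point at least twice a week") and group 4 all men, so a group effect is partly mixed with sex. With assumed group variances of 0.02, 0.05 and 0.10, the per-person sex test rejects 6%, 7% and 9% of the time. A fixed focus-group factor restores about 5%, at a price. Take five groups of 8, the other three half men and half women. The unadjusted sex contrast uses 20 against 20; for a 0.9 SD difference the noncentrality is 0.9 × √(20/2) = 2.85 and power is 79% (38 df). With the factor, groups 3 and 4 drop out, leaving 12 against 12: 0.9 × √(12/2) = 2.20 and power is 57% (34 df).

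**The case against.** **The layout may avoid the problem.** Section 7.1.2.3.2 is compatible with each food being ranked under only some labels. If each person ranks one food per label, then a subgroup test for one label and a food contrast within one label both use one answer per person, and chi-square is valid there. This stands. Label contrasts would still be repeated within a person. The questionnaire is in an appendix outside the supplied text, so the number of rankings may be fixed there and cannot be called missing.

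**The scope of the test is unclear.** By category most directly means food category and subgroup. A reader might infer that labels are also compared by chi-square; the text does not say so.

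**The size is assumed.** The document gives no correlation, and at zero correlation the error disappears. Zero is implausible for a skill task, but every figure above is an illustration.

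**Stronger readings do not hold.** A reader might conclude that any test using several answers per person is invalid. That is wrong: Cochran's Q, Friedman and repeated-measures tests use them correctly. Nor does chi-square always give too many false positives; in two of the contrasts it gives too few. Error rates above 40%, which arise if 30 answers per person are pooled at ICC about 0.2, need a layout that the 26 items do not support at one ranking per item.

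**Little depends on it.** The tests are described as exploratory, and no decision in the document uses their p-values. This is why the point is minor.

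**Conclusion.** The point holds as a minor one. Ordinary chi-square has the wrong error rate in every test to which a person contributes more than one correlated answer, and the design allows such tests in Phases 1 and 2. Under the stated assumptions, subgroup false positives are about 6.5%, 8% and 9% with two pooled answers and 10%, 15% and 19% with five. A five-food contrast within one label falls to 3%, 2% and 1%. The valid alternatives stay near 5% in the main settings. One limit is known: when the person-by-label variance (0.7) sits in just one of six labels, the per-person label tests reject 6 to 8% of the time.

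A reader might infer that the choice of the two labels or the Phase 3 trial is compromised. The document does not support this. The percentages themselves do not change, 7.2.2 has no significance rule and also weighs the focus groups, and Phase 3 has its own outcome and analysis.

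**What to change.** In 7.1.2.6.1, say which comparisons the test covers. Wherever a person contributes more than one answer to a test, replace chi-square by a method with the person as the unit:

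- **Subgroups:** compare the per-person number correct.
- **Labels, several foods per label:** a repeated-measures or Friedman test on per-person scores. If rankings are incomplete, use a logistic mixed model with person and person-by-label effects (its error rate was not simulated here).
- **One binary answer per person per condition, complete data** (for example, five foods within one label): Cochran's Q with McNemar follow-up.
- **One answer per person in the test:** keep chi-square.

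State that Phase 2 follows the same rules. Adjust for focus group at most as a sensitivity analysis, because a fixed factor removes the two single-sex groups from the sex contrast and costs power.

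The cost is analysis wording only. The data, questionnaire, sample and Phase 3 stay as they are.

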##### **7.1.2.6.2 Analysis of qualitative data**

Cuartel will use audio recordings to transcribe the complete text of each performed group. Transcriptions will be organized in categories of information, generation units of descriptive, interpretative or inferential meaning that facilitate the analysis and interpretation of the results, first through the analysis and comparison within categories of meaning and later inter categories. Appendix 4 shows the arrays of results to use according to the interest categories

### **7.1.3 Stage 3. Design of alternative of Front of Pack Labels**

Based on the results of previous stages, an image designer will be asked to design three front of pack labeling alternatives considering the language and design elements identified as relevant for front-of-pack labeling. The specific guidelines for the design of these proposals will be prepared by the research team in collaboration with Cuartel.

## **7.2 PHASE 2. RE-DESIGN OF THE LABELLING PROPOSALS**

### **7.2.1 Stage 1. Exploration of acceptability and understanding**

During this stage, acceptability and objective understanding of the labels designed by the research team will be evaluated using the same methodology as the previous phase. In other words, qualitative (focus groups) and quantitative (questionnaire) methodologies will be used to evaluate acceptability and understanding of the new proposals of Front of pack labelling.

### **7.2.2 Stage 2. Re-design of the labelling proposals**

The research team will select the two labelling proposals best evaluated in terms of acceptability and understanding. For this purpose, the results of the focus groups and the questionnaire will be considered. If needed, the design team will be asked to work on those aspects of the labels that consumers found unacceptable or not understandable during the focus group, with the aim to develop two revised proposals.

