## 3 RESEARCH QUESTION

---

What FoPNL system has the best acceptability and understanding for healthy food selection in Mexican population?

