### **5.2 SPECIFIC OBJECTIVES**

1. To design alternatives of Front of Pack Labels that are easy to understand and useful in guiding healthy food choices among Mexican consumers.
  - a. To explore how several nutrient profiling systems classify a sample of food products currently available in the Mexican market.
  - b. To explore the acceptability and understanding of Front of Pack Labelling Systems used in the international food market in a sample of Mexican consumers living in urban areas.
  - c. To identify the graphic and language elements of the labelling systems that facilitate the understanding of the message of the labels towards healthy food selection.
  - d. To design Front of Pack labeling proposals considering the graphic and language elements identified in the previous step.
2. To identify which of the proposed labels has the best performance, in terms of acceptability and objective understanding, in a sample of Mexican consumers.

- a. To explore the acceptability and understanding of Front of Pack Labelling Systems used in the international food market in a sample of Mexican consumers living in urban areas.
3. To evaluate the efficacy of the two best labelling proposals to promote healthy food choices using an on-line shopping simulation in a sample of Mexican consumers.

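### Objective 2 asks which label performs best, but the planned comparison between labels is raw percentages from about 25 to 50 people, with no interval or clearly specified test for label differences

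*Combined protocol and SAP*

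**What the plan says.** The research question (section 3) is "What FoPNL system has the best acceptability and understanding for healthy food selection in Mexican population". Specific objective 2 (section 5.2) is "To identify which of the proposed labels has the best performance, in terms of acceptability and objective understanding". Both ask for a conclusion about labels relative to one another.

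The analysis is in section 7.1.2.6.1. For acceptability, it gives the share of participants choosing each label. For understanding, "the percentage of correct responses by labelling system, will be calculated". These figures are then broken down by food category and subgroup, and chi-square tests are named for differences by category. Section 7.2.1 says that the new proposals "will be evaluated using the same methodology as the previous phase".

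On size, section 7.1.2.1 says "There will be a total of five focus groups with an average of 5 to 10 participants each". Section 7.1.3 asks a designer to "design three front of pack labeling alternatives". Section 7.2.2 then states: "The research team will select the two labelling proposals best evaluated in terms of acceptability and understanding". It adds: "For this purpose, the results of the focus groups and the questionnaire will be considered". It also allows the retained labels to be revised before Phase 3.

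**The concern.** A percentage per label always produces an order, whether or not the labels differ. The plan gives no interval for the difference between two labels, no smallest difference that would count, and no way to report that labels could not be told apart. Followed as written, it could present a chance ordering as the answer to objective 2.

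Phase 3 cannot correct this. Its outcome is the nutritional quality of the basket, with energy and nutrient content as secondary outcomes (section 7.3.5). It does not measure understanding or acceptability, the third proposal is no longer present, and the two retained may have been altered. The limitations (section 9) cover representativeness, online response and the simulated setting, but not the precision of Phase 2. The expected results and the justification (section 4) offer the evidence on understanding and acceptability to decision makers, so the wording of that result matters.

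**Working it through.** The documents give no sample-size, power or error-rate figure for Phase 2, so there is none to reproduce. The 273 per group in section 7.3.7 concerns the Phase 3 outcome.

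**Inputs from the documents**
- People: 5 × 5 = 25 to 5 × 10 = 50 (section 7.1.2.1, carried over by section 7.2.1).
- Labels: three (section 7.1.3).
- Response: a ranking task is correct only if all three products are in the expected order, and five food categories are tested (section 7.1.2.3.2).

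**Assumptions, not in the documents**
- Every person does all five tasks under every label, giving 25 × 5 = 125 to 50 × 5 = 250 answers per label. Section 7.1.2.3.2 does not confirm this. It gives 26 items, of which 4 + 3 + 4 = 11 are on acceptability. The remaining 15 equal 3 labels × 5 tasks, which leaves none for demographics unless items have sub-parts.
- The true rate of correct rankings is 60%.
- On the logit scale, logit P(correct) = label intercept + person effect + person-by-label effect, with SDs of about 1. Intercepts are set to give the stated average rates.

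**Hand check of the chance gap.** Treat answers as independent. The standard error of one label's percentage is √(0.6 × 0.4 / m), which is 4.4 points at m = 125 and 3.1 at m = 250. The expected range of three equal normal quantities is (3/√π) × SE = 1.69 × SE. That gives 7.4 and 5.2 points.

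**Simulation with correlated answers** (8,000 runs per setting)
- Three equal labels: the mean top-to-bottom gap is 4.8 to 8.9 points. The low end is 50 people with no person-by-label variation. The high end is 25 people with both SDs equal to 1.
- One label truly better, both SDs equal to 1:

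| People | +5 points: alone on top | +10 points: alone on top | +10 points: paired 95% interval excludes zero against both rivals |
|---|---|---|---|
| 25 | 60% | 86% | 13% |
| 38 | 67% | 92% | 22% |
| 50 | 72% | 95% | 32% |

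A repeat simulation put the last cell at up to 33%.

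- With no true difference, the paired-interval requirement is met by some label in 1 to 2% of runs.

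**The chi-square read as a between-label test.** An ordinary chi-square on pooled answers treats them as independent. Its false-positive rate at a nominal 5% is about 2 to 3% if people differ only in overall ability. It is about 9 to 13% with person-by-label variation of the size assumed above, and 26 to 32% if that variation is strong. It is not calibrated in any of these cases.

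**How often a single leader appears when the labels are equal.** For m independent answers per label this is 3 × Σ f(x) F(x−1)², with f and F the binomial probability and distribution functions. This is one minus the chance of a tie for first. With one answer per person it is 72 to 84% (25 people) or 80 to 88% (50 people), for true rates between 0.3 and 0.9. With five pooled answers it is about 87 to 93% and 91 to 95%. Strong person-by-label variation raises it to as much as 97%.

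**The case against.** The case against is substantial. Section 7.2.2 keeps two of three proposals, names no single winner, and draws on focus groups as well as the questionnaire. Phase 2 Stage 1 is headed as exploration, objective 2a is worded as exploring, and the hypothesis (section 6) is tested in the Phase 3 randomised comparison. As a screen the ranking works tolerably: under the assumptions above, a label 10 points better comes out alone on top in 86 to 95% of samples. All of this stands, and it means the selection step needs no repair.

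A reader might go further and infer that the plan declares a best label from raw percentages with no allowance for chance, and does so more than nine times in ten when the labels are equal. The documents do not support that. The selection is not based on percentages alone, and a chi-square test is named, although its target is ambiguous. The frequency of a single leader ranges from about 72 to 97% over unstated inputs. It is only the complement of a tie and rises as the sample grows, so it does not measure the weakness of a small sample.

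Nor do the expected results or the justification say that a best-understood label will be announced; they promise evidence on a variety of systems. What the objection leaves untouched is that the research question and objective 2 ask which label is best, and no planned analysis shows whether labels differ by more than chance.

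**Conclusion.** The concern holds as a mismatch between objective 2 and its analysis. Raw percentages from 25 to 50 people cannot carry a statement about which label is best understood. Chance alone would separate three equal labels by about 5 to 9 points, and a true 5-point advantage would be ranked alone on top only about 60 to 72% of the time. These sizes depend on five tasks per person per label, 60% correct, and person and person-by-label SDs of about 1, and the documents give none of these. The mismatch itself does not depend on them.

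It would be wrong to infer that the choice of labels for Phase 3, or the Phase 3 comparison, is invalid. Choosing between labels that are in truth equal does little harm in a screen, because the retained labels are then tested against a no-label control.

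**What to change.** Leave the selection in section 7.2.2 as it is. Change section 7.1.2.6.1 and the wording of objective 2:

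- Report the within-participant difference in percentage correct for each pair of labels, with a 95% interval. Use one score per person per label, or a model clustered on person (such as a logistic mixed model or GEE), in place of a pooled chi-square.
- State what the category chi-square compares.
- Describe the two retained proposals as selected for Phase 3. Say that one label is better understood than another only where the interval for that pair supports it, and call a label best only where it does so against every other proposal.
- Use the same restraint for acceptability shares.
- State how many ranking tasks each participant completes under each label, since the paired analysis depends on it.

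The cost is some wording and a few intervals on data already planned, with no extra participants and no change to Phase 3. The drawback is that Phase 2 will often have to report that no label was shown to be best. Under the assumptions above, a true 10-point advantage would be shown against both rivals only about 13% of the time with 25 people and 32 to 33% with 50.
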